## 4.0 Study Intervention(s)/Interaction(s)

### 4.1 Description:

The TWM intervention has two major components: an individualized self-monitoring component and a social support component. For the self monitoring component, users can enter their daily ART medications into a private profile page. Many men will only take one dose of medication per day, while others may take multiple doses. Men can then customize how they would like to set up SMS medication reminders. Based on the participant's preferred time, a daily text message will be sent 5 minutes after the participant is supposed to take their medication. Participants can choose from standardized language from our website for this text message or they can customize the language for further discretion. The standard language will ask: "Have you taken your dose today? Respond "1" yes, respond "2" no skipping today, respond "3" remind me again in an hour." Participants will then be asked how they feel at the moment and will be given a choice of

PROTOCOL TITLE: A Technology-Delivered Peer-to-Peer Support ART Adherence

Intervention for Substance-using HIV+ Adults

VERSION DATE: 4/2/18

5-6 common emotions (happy, sad, anxious/worried, angry, tired). Responses collected via text message will be synched directly to participants' private profile page and they will be able to view their adherence and mood tracking throughout the course of the intervention. Once a week we will ask participants to log-in to the website directly to report substance abuse for the week. Participants will be asked to check which days they used alcohol; which days they used marijuana; and which days they used other drugs. Participants will be able to view their medication adherence, mood, and substance use for the entire week on the same screen.

The social support component of the website is a social network page similar to Facebook, but with targeted content being placed in the feed. TWM intervention staff will create approximately 300 "Thrive Tips" based on addressing barriers identified in the IMB-AAQ survey (all participants take the IMB-AAQ at baseline and this survey is included in the attached appendices under Measures) . Participants will see 4 unique Thrive Tips per day posted to their daily feed. If a participant has identified specific barriers to medication adherence (e.g. fear of someone seeing them take their medications), the Thrive Tips associated with their identified barriers will be highlighted differently in their personal feed to draw more attention to them. Participants can comment on the Thrive Tips to start discussions with other members, or they can start their own topics of discussion. Research staff may also pose questions to the group to spur discussion among members. Research staff will monitor the page daily for hostile interactions or misinformation. Hostile interactions can be flagged by users or admins and removed. In the pilot trial of TWM, admins found that other users would often correct misinformation in a prompt manner and research staff rarely had to step in. Our intention is for users to create community throughout these interactions and also to demonstrate leadership in the group by either starting topics, sharing information, and/or correcting misinformation with minimal guidance from research staff. Participants will be able to privately message with research staff through the TWM website. Participants will not be able to privately message each other through the website. All 300 Thrive Tips will be made available over the course of the first 75 days of the intervention. After the first 75 days, the intervention group will take another IMB-AAQ through the TWM website to see if their medication adherence barriers have changed. The 300 Thrive Tips will be re-ordered and released 4 per day for the remaining 75 days of the intervention.

## 5.0 Procedures Involved

### 5.1 Study Design:

Based in the results of the TWM pilot study, we will evaluate the TWM intervention in a randomized controlled efficacy trial (RCT). Recruitment

PROTOCOL TITLE: A Technology-Delivered Peer-to-Peer Support ART Adherence

Intervention for Substance-using HIV+ Adults

VERSION DATE: 4/2/18

will be stratified by drug use, such that half of participants will report illicit drug use in the prior 5 months at baseline (see inclusion criteria in Section 9.1). MSM will be recruited in New York City metropolitan area, screened, and randomized to receive either the TWM intervention or HIV-information only control condition. VL, validated self-report ART adherence, and drug use will be collected at baseline, immediate post-intervention, and 6- and 11-month post intervention to test the study hypotheses.

## 5.2 Study Procedures:

Partners:

Key partners for the study and their roles are as follows:

- CHEST, Subcontractor – CHEST will manage recruitment, screening, training, and retention of participants. They have received IRB approval through the City University of New York.
- [name], Co-Investigator and Subcontractor – [name] will only have contact with participants in extenuating circumstances (if multiple people from the UMN study team are not available, which has not occurred thus far in the study) and will otherwise only have access to de-identified data. She has received IRB approval through the University of Michigan.
- [name], Collaborator – [name] will conduct qualitative data analysis and will only have access to de-identified data. She will receive IRB approval through Portland State University.

Usability Testing:

Before the full RCT begins, we will conduct pilot/usability testing with 10 HIV positive men recruited by CHEST staff in New York City. Participants recruited for usability testing will be scheduled for an in-person appointment at CHEST. At this visit they will sign the consent form and take the baseline survey using Qualtrics. CHEST staff will then give the participant a unique username and password for the TWM website and ensure they can log-in.

The participants will then be given a task list of actions they need to perform on the website (i.e. start a discussion topic, share and comment on a Thrive Tip, create a profile, etc.) over the course of 1-2 weeks. After that period is over, they will return to CHEST to complete a 45 minute interview with the PI, project coordinator, and a CHEST staff member. While a CHEST staff member will be present to facilitate, an in-person telephone interview between the project coordinator and the participant will be held. Both the task list and interview questions are attached to this application (Website Tasks and Usability Interview Questions). The interview is intended to illicit feedback on programmatic components, not to draw out personal information regarding medication adherence, sexual behaviors or substance

PROTOCOL TITLE: A Technology-Delivered Peer-to-Peer Support ART Adherence

Intervention for Substance-using HIV+ Adults

VERSION DATE: 4/2/18

use. Responses from usability testing will be used to complete development of the TWM website and make any final changes before launch.

Randomized Clinical Trial:

Persons interested in the study will be scheduled for an in-person appointment at CHEST to complete the screener items, baseline VL blood draw, and urine samples for drug use. Participant-identifying information, including informed consent forms, locator forms, or any file linking ID numbers to names are kept in locked cabinets at all times at CHEST.

Secure (i.e., using SSL encryption and online survey software supported by the University of Minnesota) online survey software will be used to collect baseline and follow-up self-reported data, and will be managed by research staff at the University of Minnesota. Participants may be asked to sign a HIPPA Authorization/Release form, that (if signed) will grant permission for research staff to obtain the participant's medical record. As stated in the consent form, HIPPA authorization will only be sought in the rare event that viral load is unable to be evaluated or requires confirmation.

Participants will be contacted and informed that their healthcare provider is going to be contacted before such contact is made. Participants are not required to sign the HIPPA Authorization/Release form.

**Biological Data Acquisition and Transmission.** Blood draws will be collected at CHEST during the baseline, immediate post-intervention, 6-, and 12-month post-intervention visit to assess the effects of the TWM intervention on viral load, the most important biological marker for adherence. Blood will be drawn by a certified phlebotomist at CHEST and analyzed by Quest Diagnostics. Plasma VL is considered undetectable at <20 copies/mm^3 and we will provide test results to participants after each visit. We have successfully used this procedure with MSM in prior studies. The urine sample will be tested for metabolites of methamphetamines, cocaine, ecstasy, marijuana, and opiates using the Integrated E-Z Split Key Cup II- 5 Panel (Innovacon Laboratories). Though studies have consistently supported the validity of self-reported drug use assessment instruments, research has shown that when individuals are informed that their self-reported behavior will be validated through biological measurement, they are more likely to accurately report their behaviors. All biological specimen samples collected will be destroyed as soon as they are tested. Results from the blood and urine screens will be entered into Qualtrics and tied to the participant's study ID and will never be included in the person's medical record. Attached to this application is a screenshot from CHEST regarding how they enter HIV outcomes into Qualtrics (Sample HIV Outcomes Measures); please note that the University of Minnesota logo will appear on all TWM survey screens.

PROTOCOL TITLE: A Technology-Delivered Peer-to-Peer Support ART Adherence

Intervention for Substance-using HIV+ Adults

VERSION DATE: 4/2/18

Men who meet eligibility criteria will be guided through the consent process. Trained research staff at CHEST will meet in an assessment room with participants and will be available to answer any questions on the consent form. Signed paper consent forms will be stored in a separate, locked file cabinet at our research center, CHEST. Next, they will complete a computer-assisted baseline survey (using Qualtrics, which is online survey software supported by the University of Minnesota) which is anticipated to take 30-45 minutes. The baseline survey will include questions about medication adherence, engagement in care, demographic characteristics, social support, mental health, and intervention content and features.

Following well-established security protocols by this research team, data will be stored electronically, with identifying information (e.g., name, e-mail address, contact information) stored separately on a secure server from other responses. Identifying information and other data will be linked by a unique computer-generated number that will be kept in a third table and stored separately from the other two tables. The PI, the project statistician, the project coordinator, and key CHEST staff involved in enrollment and retention will have access to identified data. Other team members will have access only to the de-identified dataset.

Next, men will be randomized to the TWM intervention or control group using a blinded randomization process. The sample will be stratified by recent drug use and non-recent drug use. Those assigned to the TWM intervention will be shown example webpages of the intervention, given basic training on how to navigate the intervention, and given the opportunity to ask questions they have about the website. Control condition assigned participants will be shown example webpages they will receive during the intervention period.

After the baseline visit, participants will have access to the TWM or control intervention components. Those in the control arm will receive weekly emails with links to web pages containing information on living with HIV and tips for improving quality of life. These web pages will not be specifically focused on improving medication adherence. Control participants will receive approximately 25 emails of unique content over the course of five months.

Upon entering the TWM intervention, men will be guided through a series of pages in which they will create a unique username (not containing identifying information) and password to use throughout the study. Men will be able to choose from pre-designed icons for a profile image that will accompany their username when they post on the TWM website.

Participants in the treatment arm will have access to the full intervention for 5 months. After 5 months, participants will no longer have access to the social support component of the website and they will no longer receive SMS reminders. They will still have access to the Thrive Tips and their self-monitoring personal profile page while the website is online. The TWM

PROTOCOL TITLE: A Technology-Delivered Peer-to-Peer Support ART Adherence

Intervention for Substance-using HIV+ Adults

VERSION DATE: 4/2/18

intervention website is currently being developed. Screenshots from the pilot trial of TWM (NIH R34 MH083549) are attached to this application (Appendix E: Screenshots from TWM Feasibility Trial). The intervention for the full-scale RCT is modeled after the pilot screen shots.

### 5.3 Follow-Up:

After the intervention period, men will be contacted by CHEST study staff to schedule an in-person appointment to complete the immediate post-intervention survey (also using Qualtrics), VL blood draw, and drug urine screen. The same procedure will be used to schedule men for their 6- and 12-month post-intervention visits. If a participant moves out of the area served by CHEST, they will be offered the option to consent to take any remaining follow-up surveys remotely, and to complete any remaining viral load tests with their healthcare provider or at a central lab and have the results sent to CHEST.

## 6.0 Data Banking

The following identifiers are collected and maintained during the duration of the study: names, telephone number, birthdate, and email address. It is necessary to record identifiers since payment to subjects will be through Amazon that will be sent to their e-mail accounts. In addition, such information will be collected to successfully enact the retention protocols described in the grant proposal.

Participants demographic and survey data will be identified by a unique number. The identification number will not be linked to the participant's identity or contact information in any way. The contact information will be stored in a separate electronic file from the participant's demographic and survey data, with the two files being linked by a separate "linking file" stored in a separate location.

Identifiable study data will be destroyed 1 year after the completion of the study. We established this timeframe in the event participants have follow-up questions regarding their participation in the study. De-identified study data will be kept for 7 years after the completion of the study, which is in accordance with NIH policy. Three copies of the de-identified dataset will be maintained (a working one and two archived at different sites).

## 7.0 Sharing of Results with Participants

Results will be shared with participants in several ways. First, we will publish the results of studies resulting from this study. We will attempt to publish them in Open Access journals (as we did with the results from Aim 1) so that anyone may access those articles. In addition, we will make available a summary of study results to participants who request it.

Upon request, results of viral load tests will be shared with participants by CHEST staff.

## **8.0 Study Duration**

Individuals in the intervention arm will have access to the site for 5 months, and will complete follow up after 12 months. The total anticipated duration of the study, including analysis is from 7/1/15-5/31/20.

## **9.0 Study Population**

### **9.1 Inclusion Criteria:**

- 1) 18+ years of age;
- 2) Male gender;
- 3) Sex with 1+ men in the prior year;
- 4) Diagnosis of HIV and currently prescribed ART;
- 5) Self-reported detectable VL in past 12 months OR self-reported problems with HIV medication adherence;
- 6) Residing in the New York City metropolitan area and availability meet with project staff at each assessment time point; and
- 7) English-speaking (since the intervention will be in English).
- 8) Self-reported recent drug use (the sample will be stratified by recent drug use and non-recent drug use)

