# 3.0 Study Endpoints/Events/Outcomes

## 3.1 Primary Endpoint/Event/Outcome:

**Primary Aim 1:** Determine the efficacy of the *TWM* intervention to increase the proportion of virally suppressed HIV-positive MSM at post-intervention time points.

**H1:** A higher proportion of participants in the TWM intervention than control participants will have undetectable VL at post-intervention time points.

**Primary Aim 2:** Assess whether the *TWM* intervention is most beneficial for HIV-positive MSM who report recent drug use at baseline compared to HIV-positive MSM who do not.

**H2:** Recent drug-using participants in the TWM intervention will demonstrate greatest improvements in VL and self-reported ART adherence at post-intervention time points compared to non-drug-using participants.

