### 3.3. Additional information about study design and endpoints

Primary aims (Aims 1 and 2) are to examine the efficacy of the online and mobile-enabled TWM intervention in a full-scale randomized controlled trial. HIV-positive adults (all men who have sex with men [MSM]) with detectable HIV viral load (VL) residing in New York City will be randomized to receive the TWM intervention or an information-only HIV/ART intervention for a 6-month period. Recruitment will be stratified by recent drug use, such that half will report recent illicit drug use. HIV VL, validated self-reported ART adherence, and intervention utilization measures will be collected at baseline, post-intervention, and 6-, and 12-month follow up. We hypothesize that participants in the TWM intervention will demonstrate significant improvements in self-reported ART adherence and VL at each follow-up time point compared to control participants, with greatest improvements among recent drug users.

We will use an experimental research design to assess the effects of the TWM intervention on HIV VL and self-reported ART adherence among the total sample, drug-using participants, and non-drug-using participants. Data collected from participants will only be used for the purposes of this study. Data will be collected in the form of biologic specimens (blood AND urine) and computerized surveys to assess socio-demographic variables, psychological measures, and behavioral measures (e.g., drug use, ART adherence). Biological specimens and computerized surveys will be collected on-site at the Center for HIV Educational Studies and Training (CHEST) at Hunter College in New York City (NYC).

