### **9.3 Screening:**

Persons interested in the study will be scheduled for an in-person appointment at CHEST to complete the screener items, baseline VL blood draw, and urine samples for drug use. Those that meet the inclusion criteria and do not meet the exclusion criteria will be guided through the consent process and randomized.

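### Inclusion criterion 8 lists a stratification factor, recent drug use, as an entry requirement, which contradicts the two-stratum design and Primary Aim 2

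*Protocol*

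**What the plan says.** Protocol 9.1 has eight numbered inclusion criteria. The eighth reads "Self-reported recent drug use (the sample will be stratified by recent drug use and non-recent drug use"). Protocol 9.3 states how the list is used: "Those that meet the inclusion criteria and do not meet the exclusion criteria will be guided through the consent process and randomized".

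The rest of the protocol describes a mixed sample. Section 3.3: "Recruitment will be stratified by recent drug use, such that half will report recent illicit drug use". Section 5.1 says the same with a time window, and points back to the eligibility list: "such that half of participants will report illicit drug use in the prior 5 months at baseline (see inclusion criteria in Section 9.1"). Section 5.2, on randomisation: "The sample will be stratified by recent drug use and non-recent drug use". Primary Aim 2 in 3.1 asks whether the intervention is "most beneficial for HIV-positive MSM who report recent drug use at baseline compared to HIV-positive MSM who do not", and 17.1 tests this by adding self-reported drug use over the past 5 months and its interaction with intervention and time. The exclusion list in 9.2 has seven items and none concerns drug use. The Study Summary gives the population as HIV-positive MSM without restricting it to drug users, although the study title refers to substance-using adults.

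**The concern.** Eligibility criteria are operative rules, and staff apply them to one man at a time. Under 9.3 each man must meet the inclusion list, and a man with no recent drug use does not meet item 8. The bracket in that item describes the sample as a whole; it does not say that a man without recent use is eligible. Section 5.1 makes this harder to resolve, because it cites 9.1 as the source for the half-and-half split, and 9.1 contains no split.

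Drug use is both the stratification factor and the moderator in a primary aim. Any loss of non-users at screening removes part of the comparison group for H2 and shifts the Aim 1 population towards drug users. If non-users are instead enrolled as planned, the trial carries a large block of men who, on paper, fail a listed criterion.

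**Working it through.** **1. The plan's own figure.** Section 17.2 gives 200 per arm, 60% versus 46% undetectable, and a detectable difference of about 14 points. It states no power level. The SAP sets significance at 0.05 without giving sidedness; I assume two-sided. With pooled variance under the null:

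- Mean proportion = (0.60 + 0.46)/2 = 0.53; √(2 × 0.53 × 0.47) = 0.7058; √(0.60 × 0.40 + 0.46 × 0.54) = √0.4884 = 0.6989.
- n per arm for 80% power = [(1.960 × 0.7058 + 0.8416 × 0.6989)/0.14]² = (1.9716/0.14)² = 198.3, so 199.
- Power at 200 per arm = Φ[(0.14 × √200 − 1.960 × 0.7058)/0.6989] = Φ(0.853) = 0.803.

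The stated figure is reproduced at 80% power. No drug-use term enters the calculation, so the 14 points do not depend on how item 8 is read.

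**2. The sections side by side, for a man who reports no recent drug use.**

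| Protocol section | Consequence for him |
|---|---|
| 9.1 item 8, main clause | Fails an inclusion criterion |
| 9.1 item 8, bracket | Belongs to one of two strata in the sample |
| 9.3 | Randomised only if the inclusion list is met |
| 9.2 | Not excluded |
| 3.3, 5.1 | Part of the half who are not recent users |
| 5.2 | Has his own stratum at randomisation |
| 3.1 Aim 2/H2, 17.1 | Needed as the comparator |

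Only the main clause of item 8, acting through 9.3, keeps him out.

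**3. What each reading gives.**

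- Literal enforcement: 400 users and 0 non-users. The drug-use-by-condition contrast has no comparison group and cannot be estimated.
- As intended: 400 × 0.5 = 200 users and 200 non-users. The contrast can be estimated, but about 200 randomised men fail item 8.

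**4. What uneven enforcement would cost (illustration only).** The documents give no effect sizes by drug use. Assume 60% versus 46% in users, 60% in both arms in non-users, 1:1 allocation within strata, and a two-sided 5% Wald test on the difference between the two risk differences. Power ≈ Φ(0.14/SE − 1.960).

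- 200 users and 200 non-users (100 per cell): SE = √[(0.4884 + 0.48)/100] = 0.0984; power 0.30. The difference in effects detectable with 80% power is (1.960 + 0.8416) × 0.0984 = 0.276, about 28 points.
- 300 and 100: SE = √(0.4884/150 + 0.48/50) = 0.1134; power 0.23.
- 380 and 20: SE = √(0.4884/190 + 0.48/10) = 0.2249; power 0.09.

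Under these assumptions Aim 2 has little precision to spare even at the planned split.

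**The case against.** The strongest reply is that nobody reading the whole protocol would think non-users are barred. Item 8 itself says both groups are in the sample; 3.3, 5.1 and 5.2 repeat it; the Study Summary does not restrict the population; and the exclusions follow inclusion items 1 to 7 with nothing on drug use. The punctuation points the same way: the conjunction comes after item 6 and item 7 ends with a full stop, so item 8 looks like an appended note on stratification. One experienced centre does the recruiting and screening, with weekly calls to the study team. The screener is not among the documents, so it cannot be said to reject non-users.

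All of this stands as evidence of intent. It defeats the stronger reading that a reader might infer from 9.1 and 9.3 alone, namely that the trial enrols drug users only and Aim 2 cannot be answered. That reading drops half of item 8 and sets aside four other sections, and nothing in the documents shows that it was applied.

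The reply does not remove the contradiction. Clear intent elsewhere does not change what 9.3 requires, and under the intended reading half the sample still fails a listed criterion.

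Two smaller matters carry little weight. Item 8 gives no look-back period, but the substance-use measure in 3.3, and 5.1 and 17.1, all give 5 months. The SAP's split by baseline urinalysis cannot show that non-users were enrolled: by the SAP's own account the drugs it counts are detectable for 1 to 4 days, so a recent user can test negative.

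**Conclusion.** The eligibility list is wrong as written and should be corrected. It is a misplaced stratification factor in an operative rule; the two-stratum design itself is stated clearly and consistently elsewhere.

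The certain consequence is one of two things, depending on how staff apply the item: non-users turned away (all of them, if enforcement is strict), or about 200 of 400 randomised men recorded as not meeting a listed inclusion criterion. The 200 rests only on the planned half split. An empty H2 comparison group is conditional on literal enforcement and is not a finding about what happened. The interaction power figures rest on assumed effects and serve only to show that losing non-users would matter. The sample size statement in 17.2 stands.

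**What to change.** - Remove item 8 from 9.1 and state there that recent drug use is a stratification factor and not an eligibility criterion.
- In 5.1, state the roughly 50:50 split directly and correct the cross-reference to 9.1.
- In 5.2, define the stratum with the definition already in 5.1 (self-reported illicit drug use in the prior 5 months), which has the same window as the analysis variable in 17.1.
- Check that the screener agrees.

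A rule for closing a stratum is not needed to cure the contradiction. The cost is a short protocol amendment, with no extra participants or procedures.

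The SAP is written in the past tense, so enrolment may already be complete. In that case, report how item 8 was applied at screening and how many self-reported users and non-users were randomised in each arm. That requires only a tabulation of baseline data.
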